6.5.1 RESCUE THERAPY

If a participant's depression symptoms worsen over the duration of the study (as measured at Assessment #2 or spontaneously reported), the participant will be referred to receive therapy. Please refer to section 2.1.3 for additional details on the safety procedure if depressive symptoms worsen.

7 STUDY INTERVENTION/EXPERIMENTAL MANIPULATION DISCONTINUATION AND PARTICIPANT DISCONTINUATION/WITHDRAWAL

7.1 DISCONTINUATION OF STUDY INTERVENTION/EXPERIMENTAL MANIPULATION

When a subject discontinues from CCT but not from the study, remaining study procedures will be completed as indicated by the study protocol. If a clinically significant finding is identified (including, but not limited to changes from baseline) after enrollment, the investigator or qualified designee will determine if any change in participant management is needed.

Discontinuation of study for a given participant will occur in the event of any of the following:

- Suicidal thoughts with specific plans and intentions (Endorse item 9 the CDI)
- The participant is hospitalized for any psychiatric symptoms
- A participant reports symptom worsening: > 25% increased CDI score (referenced to baseline)

Reasons for discontinuation will be documented, and all outcome assessments will proceed as scheduled, if possible.

7.2 PARTICIPANT DISCONTINUATION/WITHDRAWAL FROM THE STUDY

Participants are free to withdraw from participation in the study at any time upon request. An investigator may discontinue a participant from the study for the following reasons:

- Significant study intervention non-compliance, such as not engaging in the video game intervention at all (compliance will be monitored in real-time using Akili software).
- Lost-to-follow up; unable to contact subject (see **Section 7.3, Lost to Follow-Up**)
- Any event or medical condition or situation occurs such that continued collection of follow-up study data would not be in the best interest of the participant or might require an additional treatment that would confound the interpretation of the study
- The participant meets an exclusion criterion (either newly developed or not previously recognized) that precludes further study participation
- The study is suspended or canceled

The reason for participant discontinuation or withdrawal from the study will be recorded. Subjects who sign the informed consent form but do not receive the study intervention, may be replaced. Subjects who sign the informed consent form and receive the study intervention, and subsequently withdraw, or are discontinued from the study, will be replaced.

7.3 LOST TO FOLLOW-UP

A participant will be considered lost to follow-up if he or she fails to return for a scheduled visit and study staff are unable to contact the participant after at least 3 attempts for each visit.

The following actions must be taken if a participant fails to for a required study visit:

- The site will attempt to contact the participant via email to the parent and/or phone call to parent, reschedule the missed visit within two weeks, counsel the participant on the importance of maintaining the assigned visit schedule and ascertain if the participant wishes to and/or should continue in the study.
- Before a participant is deemed lost to follow-up, the investigator or designee will make every effort to regain contact with the participant (where possible, 3 telephone calls or emails). These contact attempts will be documented in the participant's study file.
- Should the participant continue to be unreachable, he or she will be considered to have withdrawn from the study with a primary reason of lost to follow-up.

- 9) Endeavor Satisfaction Survey (ESS; Subject, may be completed before and after CCT intervention) – A 5-item scale rating the participant's and participant guardian's feelings of satisfaction with the video game and its effect on participant's symptoms – approximately 1 minute.
- 10) Emotion Regulation Questionnaire for Children and Adolescents (ERQ-CA) – (Gullone & Taffe, 2012). A 10-item self-report questionnaire to assess emotion regulation (subcomponents of reappraisal and suppression) in children and adolescents. Approximately 5 minutes.

Electronic data capture:

Subjects will complete the self-report forms described above using Qualtrics. Qualtrics is an Application Service Provider (ASP) with a Software-as-a-Service (SaaS) platform for creating and distributing online surveys and related research services. The platform records response data, performs analysis, and reports on the data. All services are online and require no download software; only modern JavaScript-enabled browsers are required (no Java/JVM or Flash). Surveys are usually taken online within a web browser, with optional SMS surveys and offline methods available for smartphones/tablets. Qualtrics has been approved for the University of Michigan research community, and individual investigators access the web interface through a University of Michigan Qualtrics portal. Subjects will receive a coded link via email which will take them to the required surveys. The emailed link contains no identifiable information about the subjects, and once activated, establishes an https encrypted link with the Qualtrics server. Once completed, each survey is locked so that re-access is not permitted. We can also adapt the process for each subject, e.g. provide access on computers or tablets in the Department of Psychiatry for subjects who do wish or cannot use email. Some subjects may request paper, and, if so, paper forms will be provided.

Subjects will be asked to complete the consent form online (provided through a secure web-link sent via email) via SignNow prior to their initial evaluation. A copy of the consent will be emailed to the subject. Data will be downloaded from Qualtrics and stored on protected computers to be used for analysis.

Responses entered by subjects will be available to the clinicians working with the subjects in the study. Please note that the suicide assessment rating (C-SSRS) is administered at the screening evaluation in Assessment 1. Thus, any potentially dangerous clinical condition will be identified prior to further enrollment in the study and the participant will not continue with the current protocol or start the intervention. If suicidal ideation is endorsed at any point on self-report measure of CDI, this will be flagged in Qualtrics and a member of the study team will act accordingly on this information and in a timely fashion. Additionally, language is provided at the top of every Qualtrics page assessing clinical symptomatology (from parent- or child-report) in which the child or parent is notified that survey responses may not be read immediately by study staff and that the child or parent should contact emergency services (with numbers provided) if the parent or child is worried about the current safety of the child.

EXPERIMENTAL NEUROCOGNITIVE TASKS

During the first, second, and third visit, participants may be asked to complete a Millisecond Inquisit Web Cognitive Battery.

- Millisecond Inquisit Web cognitive battery **of assessments** will be administered electronically using an iPad, and will be completed before and after the CCT intervention, and (if applicable) again 3-months after the intervention. Tasks may include Flanker inhibitory control and attention task, Game of Dice task, Little Man Test (mental rotation), Emotional Stroop task, BIRD task (distress tolerance), and Delay Discounting task; these tasks are not specifically trained in CCT to ensure that we measure transfer of training to general cognitive control capacity, rather than practice effect on specific tasks. Composite scores may be used to index cognitive control capacity. All cognitive tasks were developed by the Adolescent Brain Cognitive Development (ABCD) Research Consortium will be completed using the Inquisit Web platform (<https://www.millisecond.com/>).

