4 STUDY DESIGN

4.1 OVERALL DESIGN

We hypothesized that cognitive training *EndeavorRx* may augment cognitive control and reduce depressive symptoms. In this study, youth with subclinical depressive symptoms (ages 9 to 17) will be recruited to complete the CCT intervention for 4-weeks. Before and after the intervention, all participants will complete semi-structured clinical assessment of depressive symptoms and a computerized evaluation of cognitive control capacity (e.g., Millisecond Inquisit Web Cognitive Battery; Zelazo, Anderson, Richler, Wallner-Allen, and Beaumont, 2013)

Recruitment will leverage a well-characterized sample from a recently completed study (“Parent study”; HUM00118950) of clinically significant anxiety, a known risk factor for emergence of later depressive symptoms in the subclinical-to-clinical range. In the Parent study, 148 youths (7-17 years) with impairing anxiety were recruited and randomized 2:1 to receive 12-week CBT or a non-active control therapy, “relaxation and mentorship therapy” (RMT); behavioral, neurobiological (fMRI), and clinical measures were collected before and after treatment. Additional participants may need to be recruited beyond the “Parent study” sample (for reasons such as: slow recruitment from “Parent study” or not enough participants from “Parent study” meeting enrollment criteria).

Up to thirty subjects from the Parent study will be recruited to complete the *EndeavorRx* intervention. The intervention will be played at home for ~25 min/day), 5x per week, for 4 weeks. Designed as an exciting, youth-friendly computer game, *EndeavorRx* engages and trains cognitive control across component processes of attention, response inhibition, shifting and working memory. Of note, *EndeavorRx* game difficulty is titrated to individual performance, and thus age; the increasing difficulty helps to reduce participant boredom and progressively train cognitive control. Adherence to prescribed training will be monitored using an Akili-provided dashboard, available to the research study team, that interfaces real-time as participants access *EndeavorRx* via their iPads. If there is no game play for ≥48 hours, a parent will be contacted in order to ensure compliance with the intervention.

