9 STATISTICAL CONSIDERATIONS

9.1 STATISTICAL HYPOTHESES

Primary Endpoint:

We hypothesize that CCT will increase cognitive control capacity (Millisecond battery composite score and individual cognitive test scores) and reduce depressive symptoms (CDI and CDRS-R scores) over the 4 week period of the intervention. Specifically, we hypothesize that CCT will improve cognitive control which will in turn improve depressive symptoms as a consequence of enhanced emotional regulation. Alternatively, our null hypothesis is that there will be no difference in cognitive control capacity or depressive symptoms immediately post-intervention as compared to pre-intervention.

Secondary Endpoint*:

We hypothesize that CCT will further increase cognitive control capacity (measured by Millisecond battery composite score and individual cognitive test scores) and reduce depressive symptoms (as measured by CDI and CDRS-R) further 3-months post-intervention than immediately after the intervention. The null hypothesis is that there is no difference in cognitive control capacity or depressive symptoms from immediately post-intervention to 3-months after the intervention.

*Secondary endpoint was optional to participants and then discontinued after protocol version 2.1 (02 April 2024).

Feasibility/Acceptability and Experimental Endpoints:

1. We hypothesize that the majority of participants will complete the intervention with at least 80% compliance.
2. We hypothesize that participants will have favorable emotions associated with game play.
3. We hypothesize that depressive symptoms will be reduced from the baseline assessment of the Parent study but that they will be slightly elevated from the post-intervention assessment in the Parent study.

The statistical tests used to test these hypotheses will be outlined later in this protocol and registered with clinicaltrials.gov.

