9.4.2 ANALYSIS OF THE PRIMARY ENDPOINT(S)

We hypothesize that CCT will increase cognitive control capacity and reduce depressive symptoms. The hypothesis will be tested using paired samples (repeated measures) t -tests (pre vs. post) for each dependent variable (CDI score and Millisecond battery composite score). Both of these dependent variables are interval variables.

Standard deviations and effect sizes will be assessed for each of these analyses.

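### The primary cognitive endpoint is not fixed: the composite is undefined and individual test scores sit under the same primary hypothesis with no multiplicity control

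*Combined protocol and SAP*

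**What the plan says.** Section 3 lists cognitive control performance after the intervention among the primary endpoints. Section 9.4.2 tests it with a paired t-test, pre versus post, "for each dependent variable (CDI score and Millisecond battery composite score"). It names a single composite there and says nothing about how it is built.

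Section 9.1 is wider. Its primary hypothesis is that training will "increase cognitive control capacity (Millisecond battery composite score and individual cognitive test scores").

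Section 8.1 is looser still. "Tasks may include Flanker inhibitory control and attention task, Game of Dice task, Little Man Test (mental rotation), Emotional Stroop task", and the list ends with "BIRD task (distress tolerance), and Delay Discounting task". On scoring it says "Composite scores may be used to index cognitive control capacity". It also says that "participants may be asked to complete a Millisecond Inquisit Web Cognitive Battery", although the next sentence and the schedule in section 1.3 treat the battery as given at Assessments 1 and 2.

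Section 9.4.1 sets two-tailed p < 0.05, gives no multiplicity rule, and deletes cases listwise when Assessment 1 or 2 data are missing.

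On content, section 4.1 says the game "engages and trains cognitive control across component processes of attention, response inhibition, shifting and working memory"; section 4.3 gives a similar list. Section 8.1 says that tasks not trained by the game were chosen so that the battery measures transfer rather than practice.

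**The concern.** A primary variable has to be computable from the plan by someone who has not seen the results. This one is not. The documents do not state which tasks enter the composite, which score is taken from each, which direction counts as better, how scores are standardised or weighted, or what happens when one task is missing. Because deletion is listwise, the choice of tasks can also change who is analysed.

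Two things are at stake. The first is the false-positive rate of the cognitive claim in a single-arm study, which has no control group to temper a chance pre-post difference. The second is the effect size: section 9.2 says the study is meant to supply effect sizes for larger trials, and one taken from a composite chosen after the fact would carry selection bias into their planning.

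There is also a narrower question of content. The protocol's own labels for two listed tasks, mental rotation and distress tolerance, do not match the processes it says are trained.

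**Working it through.** **The plan's own figure.** Section 9.2 states 32 participants for 80% power and a target of 30. It gives no effect size, SD or correlation, so 32 cannot be reproduced. Solved backwards for a paired t-test at two-sided 0.05, it implies a standardised mean change of about 0.51, with 77% power at 30. Nothing ties that value to the composite.

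**Inputs.** From the documents: six listed tasks (8.1), N = 30 (9.2), two-sided 0.05 unadjusted (9.4.1), paired t-test (9.4.2). Assumed: one score per task, equal pairwise correlation ρ between task change scores of 0.1 to 0.5, and normal change scores.

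**Step 1: false positives from an open choice.** If tests were independent, the chance of at least one false positive in m tests is 1 − 0.95^m:
- m = 6: 1 − 0.95^6 = 26.5%
- m = 7: 1 − 0.95^7 = 30.2%

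The scores are correlated, so the chance was simulated with no true effect. The number of possible non-empty task subsets is 2^6 − 1 = 63, of which six are single tasks.

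| What may be tested | Any false positive, ρ = 0.1 to 0.5 | False improvement only |
|---|---|---|
| One composite fixed in advance | about 5% | about 2.5% |
| Six scores plus their composite | 27% to 21% | 15% to 11% |
| Any of the 63 subsets | 43% to 25% | 23% to 13% |

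Simulated values vary by about one percentage point between runs. The middle row corresponds to section 9.1 as written. The last row is an outer bound.

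**Step 2: does the task mix cost power?** For an equal-weight mean of K standardised changes with task effects d_j, the composite effect is

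d = (Σd_j / K) / √((1 + (K − 1)ρ) / K).

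With K = 6 and ρ = 0.2 the denominator is √(2/6) = 0.577. With K = 2 it is √(1.2/2) = 0.775. Power is from the noncentral t at N = 30; every task effect here is assumed.

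| Scenario (ρ = 0.2) | d | Power |
|---|---|---|
| Six tasks: two improve by 0.5, four by 0 | 0.167/0.577 = 0.29 | 33% |
| Six tasks: two improve by 0.5, four by 0.25 | 0.333/0.577 = 0.58 | 86% |
| Six tasks: all improve by 0.5 | 0.5/0.577 = 0.87 | 99.6% |
| Two tasks: both improve by 0.5 | 0.5/0.775 = 0.65 | 93% |
| Two tasks: only one improves by 0.5 | 0.25/0.775 = 0.32 | 40% |

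The first row runs from 58% at ρ = 0 to 21% at ρ = 0.5. The ranking of broad and narrow composites reverses with the assumed pattern of response.

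**The case against.** Section 9.4.2 does name one composite, in the singular, and does not invite anyone to test 63. That is fair, and it is why the 63-subset figure is only a worst case. But naming a score does not define it, and 9.1 brings the individual scores back in.

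The stakes may look modest. This is a single-arm pilot; section 4.1 calls clinician-measured depressive change the primary outcome variable, and section 8.2 gives that title to the CDI. The composite is therefore at most a co-primary. That lowers the stakes, but sections 3 and 9.4.2 still give it primary status.

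A reader might infer that the battery is mostly off-target and so dilutes any real effect. The documents do not support this. Section 8.1 gives transfer as its reason for using untrained tasks, and with broad transfer a six-task composite gains power. The outcome is cognitive control, which section 2.2.2 defines through directing attention to regulate emotions and behaviour; distress tolerance could arguably belong. Game of Dice, Delay Discounting and Emotional Stroop carry no construct label in the protocol, so sorting them rests on their names. What stands is narrower: the transfer rationale does not explain why mental rotation or distress tolerance should index cognitive control.

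A reader might also infer that Flanker plus Emotional Stroop must be the composite. They are one option; any composite fixed in advance removes the selection problem.

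**Conclusion.** The concern holds as a problem of specification. The composite is undefined, sections 8.1, 9.1 and 9.4.2 disagree on what the cognitive outcome is, and nothing controls multiplicity. For the set named in 9.1, the false-positive chance is 27% to 21% instead of 5%, or 15% to 11% instead of 2.5% for false improvements. These figures assume 30 analysed participants, one score per task and a change-score correlation of 0.1 to 0.5; a choice among several scores per task could only raise them.

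Loss of power is a possibility, not a finding. It follows if the tasks outside the trained processes do not respond, and not if transfer is broad. The documents give no task-level effects with which to decide.

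**What to change.** Before any outcome data are analysed, rewrite 9.4.2 so that one composite is the only primary cognitive variable. State:
- the tasks, each justified as a measure of cognitive control;
- one score per task, signed so that higher is better;
- standardisation by the Assessment 1 SD at both visits (with Assessment 1 as the common reference, since standardising each visit to its own mean would force the mean change to zero);
- equal weights;
- a rule for a missing task.

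Move all individual scores and any remaining tasks to exploratory. Replace the permissive wording on tasks and composite in 8.1, and remove individual scores from the primary hypothesis in 9.1.

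This brings the cognitive endpoint back to about 5%. It does not settle the separate CDI test or the differing statements in 4.1 and 8.2 of which outcome is primary; those should be reconciled in the same amendment.

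The cost is wording only, and every task is still collected and reported. The downside is that a result on one task can no longer support a primary claim.

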8.2 SAFETY ASSESSMENTS

Safety assessments include the following:

- **Columbia Suicide Severity Rating Scale** (C-SSRS), Screen Version - Recent (Posner, Oquendo et al. 2007). A clinician-rated scale assessing suicidal ideation and behavior.
- **Child Depression Inventory** (CDI). A self-report assessment to rate the severity of depression symptoms in children. Total scores on this measure range from 0 to 54. Symptom worsening: > 25% increased CDI score (referenced to baseline).

Any safety-related assessments (C-SSRS administered at Assessment #1) or primary outcome measure (CDI at Assessments #1 or #2) that are missed will be reported to the IRB as a protocol deviation. We will accept a window of \pm 1 week. However, for the other assessments, missing or late assessments will not be reported as protocol deviations unless they constitute > 50% of the total assessments. These allowances should affect neither the scientific integrity nor the safety monitoring provisions of the protocol.

All SAEs will be:

- recorded on the appropriate SAE Report Form
- followed through resolution by a study clinician
- reviewed and evaluated by a study clinician.

The study will comply with IRB reporting requirements and guidelines for SAEs.

8.3 ADVERSE EVENTS AND SERIOUS ADVERSE EVENTS

8.3.1 DEFINITION OF ADVERSE EVENTS

This protocol uses the definition of adverse event from 21 CFR 312.32 (a): any untoward medical occurrence associated with the use of an intervention in humans, ***whether or not considered intervention-related.***

Any unfavorable or unintended symptom, sign, or disease associated with a medical treatment or procedure that may or may not be related to the treatment or procedure. Adverse events can be related to the intervention or to the symptoms that the intervention is intended to act on (e.g. subclinical depressive symptoms), or to another disorder (e.g. Anxiety), or they could be entirely unrelated to any of these (e.g., motor vehicle accident).

8.3.2 DEFINITION OF SERIOUS ADVERSE EVENTS

An SAE is defined as an AE that meets one of the following conditions:

- Death during the period of protocol-defined surveillance
- Life-threatening event (defined as a subject at immediate risk of death at the time of the event)
- An event requiring inpatient hospitalization or prolongation of existing hospitalization during the period of protocol defined surveillance
- Results in congenital anomaly or birth defect
- Results in a persistent or significant disability/incapacity

Any other important medical event that may not result in death, be life threatening, or require hospitalization, may be considered a serious adverse experience when, based upon appropriate medical judgment, the event may jeopardize the subject and may require medical or surgical intervention to prevent one of the outcomes listed above. Examples of such medical events include allergic bronchospasm requiring intensive treatment in an emergency room or at home, blood dyscrasias or convulsions that do not result in inpatient hospitalization, or the development of drug dependency or drug abuse/overdose or cancer.

All SAEs will be:

- recorded on the appropriate SAE Report Form
- followed through resolution by a study clinician
- reviewed and evaluated by a study clinician

The study will comply with IRB reporting requirements and guidelines for SAEs.

